White Blood Cell Count	0.002 (0.0002-0.005)	0.007 (0.003-0.012)
Neutrophil Count	0.002 (0.0002-0.003)	0.007 (0.004-0.011)
Adjusted	-0.0004 (-0.001-0.002)	0.005 (0.002-0.007)
CRP	0.003 (-0.001-0.006)	0.0005 (-0.001-0.002)
IL6	0.0004 (-0.00005-0.001)	0.001 (0.0002-0.002)
LDL	0.021 (0.0004-0.041)	-0.024 (-0.074-0.027)
Adjusted	0.013 (-0.007-0.033)	-0.040 (-0.087-0.007)
HDL	-0.012 (-0.023--0.001)	-0.027 (-0.054--0.0003)
Adjusted	0.002 (-0.007-0.012)	-0.026 (-0.048-0.004)
Triglycerides	0.054 (0.025-0.083)	0.055 (-0.020-0.1)
Adjusted	0.009(-0.027-0.046)	0.057 (-0.014-0.127)
Matsuda insulin sensitivity	-0.003 (-0.004--0.001)	-0.001 (-0.006-0.004)
Adjusted	0.0003 (-0.002-0.001)	0.086 (-0.004-0.176)
Insulin Secretion	0.001 (0.0004-0.002)	0.002 (0.001-0.004)
Adjusted	-0.0001 (-0.001 0.001)	0.002 (-0.00006-0.004)
Disposition Index	-0.0004 (-0.003-0.002)	0.005 (-0.001-0.011)
Endothelin-1	-0.0002 (-0.001-0.0003)	-0.001 (-0.002-0.0004)
PAI-1	0.002 (-0.0002-0.005)	0.0003 (-0.004-0.005)
Adjusted	-0.0004 (-0.002-0.002)	-0.001 (-0.005-0.004)

increased risk in subjects with one F allele. This will be important to explore in this proposal since HDL levels differ between African-Americans and Caucasians.

FFMI decreased as C4T ($\beta=-0.73$; CI: -1.24--0.22) and C4L ($\beta=-0.46$; CI: -0.81--0.10) copy number increased. C4S, C4A, and C4B copy number were not related to any measure of body habitus. C4T gene copy number was not related to any of the cardiovascular risk factors but relationships were found for the various C4 subtypes. Interestingly, HDL was significantly

related to all 4 subtypes and increased C4L copy number increased ($\beta=3.59$; CI: 1.19-6.00), decreased as C4S ($\beta=0.4.26$; CI: -7.50—1.02) and C4B ($\beta=-5.56$; CI: -10.3--0.87) increased and increased as C4A increased ($\beta=4.33$; CI: 1.00-7.66) (**Figure 2**). These relationships are particularly interesting in light of the relationship of C4 levels to HDL and suggest that C4 may play a role in determining HDL levels.

LDL and triglyceride levels were not associated with any of the C4 gene copy numbers. Interestingly, while increased C4L gene copy number was associated with increased HDL, it was also associated decreased insulin secretion ($\beta=-0.24$; CI: -0.44-0.05) and decreased disposition index ($\beta=-0.61$; CI: -1.14--0.08).

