Sample size: Based on our preliminary data for the F versus polymorphism and the data of Philips et al⁴⁰ site we will be able to effect size variable differences of 0.47 for the F versus S polymorphism, 0.7 for rs11569562 and 1 for rs2250656 with $\alpha=0.05$ and $\beta=0.8$ within African-Americans.

Interpretation: Our hypothesis will be proven by increased BMI, waist circumference, percent body fat, blood pressure, triglycerides, LDL cholesterol, CRP, IL-6, fibrinogen, and/or PAI-1 and/or decreased HDL, insulin sensitivity, disposition index, or reactive hyperemic responses in subjects with at least one F or one A allele and/or if the subjects with at least one allele have increased worsening over 1 year than do those without. Previous studies of the effects of complement on cardiometabolic risk in adults have found differences in some risk factors but not others although there is disagreement on the areas affected.^{11,18,20}

Specific Aim 3: To determine whether C4 gene copy number variation is associated with increased cardiometabolic risk in African-American adolescents.

Statistical methods: Robust rank order regression will be used to assess the relationship of C4 gene copy number for each C4 subtype and cardiometabolic risk. Age and sex will be included in all models.

Sample size: With 99 subjects we will be able to detect an $r=0.28$ with $\alpha=0.05$ and $\beta=0.80$ for each analysis without correction for multiple analyses. There is no literature available to assess whether an $r=0.28$ is a reasonable expectation but r -values below this are unlikely to indicate important mechanistic relationships.

Interpretation: Our hypothesis will be proven by positive relationships between C4 copy number and BMI, waist circumference, percent body fat, blood pressure, triglycerides, LDL cholesterol, CRP, IL-6, fibrinogen, and/or PAI-1 and/or negative relationships to HDL, insulin sensitivity, disposition index or reactive hyperemic responses. The main limitation of this study is sample size. No studies have been done to identify expected effect sizes for these variables in African Americans. As indicated for rs11569562 we will be able to detect differences with an effect size of 0.7 and for rs2250656 with an effect size of 1. Smaller differences with physiological significance could be present but may not be statistically significant in this population.

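### Aim 3 counts its hypothesis as proven by any one of 14 markers moving in one direction for undifferentiated C4 copy number, although the plan's own evidence differs in direction by subtype

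*Combined protocol and SAP*

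**What the plan says.** - **Aim** (Data analysis, Specific Aim 3): "To determine whether C4 gene copy number variation is associated with increased cardiometabolic risk in African-American adolescents". Increased risk is the outcome of interest, but the aim does not say whether high or low copy number carries it.
- **Statistical methods:** robust rank order regression, adjusted for age and sex, to "assess the relationship of C4 gene copy number for each C4 subtype and cardiometabolic risk".
- **Sample size:** 99 subjects detect r=0.28 at α=0.05 with 80% power (printed as β), "for each analysis without correction for multiple analyses". Sidedness is not stated.
- **Interpretation:** "Our hypothesis will be proven by positive relationships between C4 copy number and BMI, waist circumference, percent body fat, blood pressure", continuing with triglycerides, LDL, CRP, IL-6, fibrinogen and PAI-1, and/or negative relationships to HDL, insulin sensitivity, disposition index or reactive hyperemia. Every listed result means more copies, more risk. Subtypes are not separated.
- **Preliminary Studies, Complement genetics:** "C4T gene copy number was not related to any of the cardiovascular risk factors but relationships were found for the various C4 subtypes".

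The rest of the Interpretation, the Limitations and the Future Directions do not say how a significant result in the other direction would be classed. Future Directions refers to significant relationships without giving a direction.

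**The concern.** The decision rule is narrower than the question in one respect and looser in another.

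It is narrower because an association of low copy number with higher risk would answer the aim but is not listed as support. Whether it counts would have to be settled after the data are seen. This is a live possibility: the Background cites just such an association for C4B, and the preliminary HDL results for C4L and C4A run that way.

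It is looser because, read as written, one significant marker for one subtype in the listed direction is enough to call the hypothesis proven, and no allowance is made for the number of tests.

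What is at stake is the stated conclusion of Aim 3. The regression estimates, intervals and p-values are the same under any reading.

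**Working it through.** **1. The plan's own figure.** Fisher z for a correlation: n = [(z for α + z for power) / atanh(r)]² + 3, with r=0.28 and 80% power.
- Two-sided 5%: n = 97.8, so 98. The stated 99 reproduces; power at 99 is 80.5%.
- One-sided 5%: n = 77.7, so 78. This does not reproduce.

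The sample size is thus consistent with two-sided testing. That is an inference, since the plan does not state sidedness.

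**2. Direction of the plan's evidence, set against the rule.**

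| Evidence | Where | Against the rule? |
|---|---|---|
| HDL rose with C4L: 3.59 (1.19 to 6.00) | Preliminary Studies | against |
| HDL rose with C4A: 4.33 (1.00 to 7.66) | Preliminary Studies | against |
| Low C4B, higher cardiovascular risk | Background, Complement genetics | against |
| HDL fell with C4S: −4.26 (−7.50 to −1.02) | Preliminary Studies | fits |
| HDL fell with C4B: −5.56 (−10.3 to −0.87) | Preliminary Studies | fits |
| Disposition index fell with C4L: −0.61 (−1.14 to −0.08) | Preliminary Studies | fits |
| More C4L, impaired endothelial function (no estimate printed) | Significance, item 3 | fits |
| Low C4L, greater longevity in Germans | Background, Complement genetics | fits |

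The C4S estimate is misprinted; −4.26 is the midpoint of its interval. C4L is mixed within itself, and C4B points one way for HDL and the other in the cited literature. Under Complement genotypes, total C4 equals C4A plus C4B and also long plus short, so opposite signs within a pair are plausible.

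**3. Strength of the two inverse HDL results.** Here inverse means opposite to the rule; the coefficients themselves are positive. z = estimate / [(upper − lower)/3.92].
- C4L: 3.59 / (4.81/3.92) = 2.93.
- C4A: 4.33 / (6.66/3.92) = 2.55.

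Partial r = z/√(z² + 71), taking 75 subjects and 71 degrees of freedom, gives 0.33 and 0.29. With 99 subjects, each pair on its own would be significant in about 92% and 83% of studies at full effect, and 37% and 30% at half effect.

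**4. Effect on the whole rule.** The rule covers 10 adverse and 4 protective markers, 14 in all; with four subtypes that is 14 × 4 = 56 tests (70 if total C4 is added). Simulation assumptions: the four preliminary HDL effects carry over, nothing else is real, markers correlate 0 to 0.5, and the members of each pair (long with short, C4A with C4B) correlate 0 to −0.8. The documents give none of these correlations. The rule is unmet while C4L or C4A is significantly inverse for HDL in:
- about 1 to 2.5% of studies at full effect;
- about 4 to 20% at half effect, the upper end with marker correlation 0.5 and uncorrelated pairs.

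**5. Chance of meeting the rule with no true effect.** Each two-sided 5% test has a 2.5% chance of a hit in the listed direction.
- Expected hits: 56 × 0.025 = 1.4.
- At least one, independent tests: 1 − 0.975⁵⁶ = 76%.
- At least one, marker correlation 0.5 (assumed, by simulation): about 54%.

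**The case against.** A directional hypothesis is legitimate under an aim that speaks of increased risk, and testing one two-sided is routine. The stated direction has a real basis: C4L with endothelial function and disposition index, the German longevity result, and HDL with C4S and C4B. The study is exploratory and cross-sectional, says so, and discloses that no correction is made. All of this stands, and it keeps the point modest.

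It can also be argued that the gap closes itself. If the list is exhaustive, an inverse result is simply not proof; if it is not, inverse results are not barred. But the plan does not say which reading applies, so the choice is left until after the results. On the exhaustive reading, the C4B association that the Background cites would go unlisted.

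Three stronger readings are tempting and are not supported:
- **That the plan excludes inverse results.** The Interpretation does not say *only*, and nothing bars reporting them.
- **That 92% or 83% of studies would reach the wrong conclusion.** Those figures are for a single subtype-marker pair. Because any one hit meets the rule, it is met in about 97 to 99% of studies at full effect and roughly 70 to 90% at half effect, often by chance in the latter case. The figures also borrow effects from 75 non-Hispanic white adolescents that were singled out as significant and so are likely optimistic.
- **That the sample size is wrong.** It reproduces.

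A final objection is that multiplicity is a separate matter and one sentence on opposite results would be enough. That sentence would settle the classification, but it would leave a rule that chance alone meets more often than not described as proof.

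**Conclusion.** The point holds as a cheap improvement. Aim 3's rule gives one direction to copy number as a whole, while the analyses are by subtype and the plan's evidence differs by subtype. It leaves unclassed a result that would answer the aim, and it calls the hypothesis proven on any one of 56 or more uncorrected tests.

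The directional gap has a small effect on the overall conclusion: about 1 to 2.5% of studies at full preliminary effect and 4 to 20% at half effect, if those HDL effects apply in African-American adolescents, which the documents do not establish. The any-hit feature matters more, with chance alone meeting the rule in about 54 to 76% of null studies, depending on how strongly the markers correlate. Neither changes an estimate, a test or the sample size.

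**What to change.** In the Aim 3 Interpretation:
1. Before analysis, state the expected sign for each subtype where there is one, by marker if it differs (as for C4L).
2. Interpret two-sided results by subtype. Report a significant result opposite to the expected sign as such: evidence of association in the other direction, not absence of support.
3. Replace *proven* with *supported*.
4. State the number of tests and show a false-discovery-rate-adjusted result beside each unadjusted one.

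**Cost:** a few sentences and one column of adjusted p-values. There are no new data, and 99 subjects and r=0.28 stand.

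**Downside:** reading both directions doubles the expected chance hits over 56 tests, from 1.4 to 56 × 0.05 = 2.8, which is why the adjusted column belongs with it. Adjustment holds the chance of any hit with no true effect to about 5%, but power falls. With Benjamini-Hochberg at 5%, 56 independent tests and only the four HDL effects real, simulated power is about 60% for C4L and 45% for C4A at full effect, and 5% and 3% at half effect. The adjusted results should therefore accompany the unadjusted ones, not replace them.

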Complement and Cardiovascular Risk in Adolescents

NCT02821104

11/5/2020

SPECIFIC AIMS

African-Americans have increased incidence of and mortality from cardiometabolic diseases, including stroke,¹⁻³ hypertension,⁴ and type 2 diabetes.⁴⁻⁶ The incidence of myocardial infarction in African-Americans may be lower than in Caucasians,⁷ but mortality is increased, particularly at younger ages. These conditions are all outcomes of the metabolic syndrome. There are clear and consistent racial differences in how the metabolic syndrome presents.^{4,8-10} The cause of these racial differences and how they affect the long term outcome of the metabolic syndrome are unknown.

Recent studies have demonstrated an important role for the complement system in the development of the metabolic syndrome and its complications. This may be particularly important in relationship to racial differences in the metabolic syndrome and its outcomes since adipose tissue both produces and responds to complement. Specifically, complement component C3 is produced by adipocytes, macrophages, and endothelial cells and adipocytes have receptors for complement components, C3a and C5a.¹¹ Beyond this C3a-desArg, a product of C3a cleavage by carboxypeptidase, increases adipocyte free fatty acid uptake and triglyceride production. Preliminary data from our laboratory clearly shows a close correlation between plasma triglyceride levels in nonHispanic Caucasian adolescents and complement C3 levels independent of obesity. The close relationship of triglyceride levels to complement has particular importance because African-Americans have reduced plasma triglyceride levels compared to Caucasians but also have increased free fatty acid levels^{12,13}. ***Thus, there is good reason to hypothesize that differences in complement activation play a significant role in racial differences in the metabolic syndrome and cardiovascular risk.***

Adult cardiometabolic diseases have their origins in childhood and adolescence. The **long-term objective** of our laboratory is to develop a full understanding of the mechanisms of cardiometabolic risk in adolescents through which therapeutic interventions may be developed. The **short-term objective** of this study is to explore adolescent racial differences in complement components C3 and C4 and their relationship to early cardiovascular risk factors. In addition, we will study racial differences in specific C3 polymorphisms and C4 gene copy number.

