Regarding complement, African-Americans have been shown to have increased C4 levels⁶⁸, differences in C4 gene copy number in relationship to lupus⁶⁹⁻⁷², and different C3 polymorphism frequencies⁷³ than Caucasians. Regarding the latter have higher C3s allele frequency compared to Caucasians (93 versus 83%).⁷³ [name] studied the relationships between complement and obesity in 189 African American (Black) and 331 Caucasian (White) adult subjects from central Ohio.^{74,75} Between race differences in C3 and C4 levels were noted with increased BMI and C4 levels and decreased C3 levels in African-Americans. In each race group, strong correlations were seen between C3 and C4 protein concentrations, C4 protein levels and gene copy number of C4, BMI and C3 concentrations, BMI and C4 concentrations, and BMI and yield of C4 protein per copy of gene. In an earlier study of Hungarian subjects, positive correlations between serum C3 levels and total cholesterol concentration and between C3 levels and triglyceride levels were seen.⁴⁴

Significance: There are three important areas of innovation in the proposed studies.

1. ***Our study will be the first to explore the relationships of C3 and C4 levels to cardiovascular risk factors in African-Americans.*** This is important follow-up to our current study of nonHispanic Caucasian adolescents (Data presented below) because of the demonstrated differences in cardiovascular disease between African-American and Caucasian adults and in cardiovascular risk in adolescents. These studies will help us determine potential mechanisms for these differences early in the course of the disease.
2. ***Our study will be the first to explore the relationship between C3 polymorphisms and traditional and non-traditional anthropometric, biochemical, and functional cardiometabolic risk factors in African American adolescents.*** No studies have been done examining the role of C3 polymorphisms on cardiometabolic risk in adult or adolescent African-Americans. Again because of the increased cardiovascular disease and risk and because of the different polymorphism frequency in African-Americans it is clearly important that this population be studied.

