3. ***Our study will be first to explore the relationship of C4 copy number variation to cardiometabolic risk in African-American adults or adolescents.*** The effects of C4 gene copy number variation of longevity have varied among different ethnic groups. As indicated below, we have found increased C4L gene copy number is associated with impaired endothelial function in nonHispanic white adolescents. Whether this relationship is present in African-Americans is unknown.

It is important that studies be done in this age group to determine the early role of complement genetics in the development of cardiometabolic risk before the onset of overt disease or other co-morbidities and their treatment confound potential relationships. ***The results of this study will help us gain a full understanding of the role of complement in increasing cardiovascular risk in African-Americans and in potentially developing genetic methods of identifying at-risk individuals.***

PRELIMINARY STUDIES

Demographics: Thirty-four of the 75 subjects were female. Mean age was 15.0 ± 1.7 years and mean BMI was 22.0 ± 5.8 kg/m²) were studied.

Complement and body habitus: Robust rank order regression analysis with was used to assess relationships between C3 and C4 protein levels, C4 gene copy number variation to body habitus, lipids, inflammation, carbohydrate metabolism, and clotting factor. Age and sex were included in all models. The cut-off point for outliers was 3 and 100 iterations were performed. Results are presented as 95% confidence intervals.

C3, C4, C3a, C4a, and C5a levels did not differ between sexes and were not significantly related to age. C3 levels positively correlated with all measures of body mass and adiposity (Figure 1). The correlation with FMI ($R^2=0.41$) was better than with FFMI ($R^2=0.22$). C4 levels were not related to any measure of body habitus. For C3a, C4a and C5a the only significant relationship was between C4a and FFMI ($\beta=9.82$, CI: 1.55-18.1).

[figure not shown]

Figure 1: Relationships of C3 levels to measures of body habitus. BMI: $\beta=35.9$; CI: 23.6-48.2; BMI%: $\beta=5.22$; CI: 3.35-7.08; Waist circumference: $\beta=15.4$; CI: 10.01-20.9; Body Fat %: $\beta=18.6$; CI: 12.5-24.7; FMI: $\beta=49.2$; CI: 33.2-65.2; FFMI $\beta=52.9$; CI: 14.9-90.1.

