Complement genotypes: C3 genetic variants including the DNA sequence polymorphisms for G102R for fast and slow allotypes, and SNPs for rs11569562 and rs2250656 that modulate C3 plasma protein levels will be typed for all study subjects. Copy-number variations for total C4, C4A, C4B, long genes and short genes of C4 will be elucidated by Southern blot analyses of genomic DNA samples digested by Pmel, Taql, PshAI/Pvull and resolved by gel electrophoresis.⁷⁴ Samples for subjects with ambiguous data will be subject to realtime quantitative PCR using five different amplicons and the results will be validated as the gene copy-numbers in each subject for total C4=C4A+C4B=long genes+short genes.⁸⁵

Cardiovascular measures, glucose and insulin: IL6, CRP, endothelin 1, fibrinogen, PAI1 glucose and insulin will be measured in the CORE laboratory. Plasma lipids will be measured in the clinical laboratory of the Wexner Medical Center.

Data analysis: **Specific Aim 1:** To determine whether there are racial differences in complement C3 and C4 levels in healthy adolescents and how they relate to cardiometabolic risk factors including triglyceride and LDL levels, inflammation, and vascular function.

Statistical methods: Complement levels from African-Americans in this proposal will be compared to those from nonHispanic whites in our current study. Eligibility criteria are identical for both studies except for race. Data will be assessed for normality using the Shapiro Wilk test ($p>0.05$ indicative of normality). Non-normal data will be log normalized if possible. Unpaired t-tests will be used to compare differences in C3 and C4 levels as well as cardiometabolic risk factor results (reactive hyperemia, augmentation index, Matsuda index, insulin secretion, lipids, inflammatory markers, and PAI-1). We anticipate age and BMI differences will be minimal but should racial differences be found analysis of covariance will be done to account for any difference found.

Robust rank order regression analysis will be used to assess relationships between C3 and C4 protein levels to body habitus, lipids, inflammation, carbohydrate metabolism, and clotting factor in each race individually and in the group as a whole. Age and sex will be included in all models. The cut-off point for outliers was 3 and 100 iterations were performed. Results are presented as 95% confidence intervals.

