Sample size: Based on data from our previous study with 100 nonHispanic white subjects and 100 African-American subjects we have power 0.8 to detect a 15% racial difference in C4 levels and 7.5% difference in C3 levels.

Interpretation: There are two major portions of this aim. The first is to determine whether there are complement levels differences between the racial groups and the second is to determine how these affect previously demonstrated racial differences in cardiovascular risk¹². The former will be easily determined by comparing complement levels in the two groups. The hypothesis that these racial differences are responsible for at least some of the cardiometabolic racial differences will be proven if when complement levels are included in the regression equation they retain significance but the racial differences are lost. Lastly, even if racial differences in complement are not found or do not account for cardiometabolic risk differences it will still be important for us to determine whether the significant effects of complement described above in nonHispanic whites are present in African-American adolescents.

Specific Aim 2: To determine whether specific C3 polymorphisms, F versus S, A>G at rs11569562 and/or rs2250656, are associated with increased cardiometabolic risk in African-Americans.

Statistical Methods: As indicated above, the C3F gene has been associated with increased risk of myocardial infarction in several populations³⁶⁻³⁸ and Phillips et al⁴⁰ reported increased cardiometabolic risk in subjects with either an A/A or A/G versus subjects with a G/G genotype for both the rs11569562 and the rs2250656 sites. For rs11569562 in a European population ~ 25% of subjects had G/G and for rs2250656 ~10% had G/G. Frequencies in the African-American population are unknown. Data will be assessed for normality using the Shapiro Wilk test ($p>0.05$ indicative of normality). Non normal data will be log normalized if possible. Unpaired t-tests with unequal sample sizes will be used for comparisons for each of the measured normal variables between subjects with at least one A allele gene and those with two G alleles assuming the data is normally distributed. Mann-Whitney U tests will be used to assess non-normal data.

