Limitations: This study is limited to studying C3 and C4 genetic differences and their relationships to differences in complement and cardiometabolic risk factors and not social and lifestyle differences between the two racial groups. An extremely interesting finding would be racial differences in complement levels without significant difference in complement genetics. This would suggest that differences in lifestyle (physical activity, socioeconomic stress) may play a significant role in causing complement racial differences. Even if no racial differences are found, these studies will still generate important information regarding the relationship of complement to cardiometabolic risk in adolescents and will indicate what areas should be explored to gain a better understanding of the racial risk differences.

Future Directions: Correlational, cross-sectional studies do not prove causation so if these results demonstrate significant relationships between complement and/or complement genetics in cardiometabolic risk then future longitudinal follow-up studies will be important. It would also be important to extend these findings to additional ethnic groups. Examining the effects of socioeconomic and cultural differences on the relationships of complement to cardiometabolic risk factors may also be of value. Our results also have potential value to inform future treatment studies to prevent or reduce cardiometabolic risk. The most immediate would be using complement genetics to potentially identify subjects at high risk for future cardiometabolic disease. Furthermore, various anti-complement therapies are being developed for use in a variety of diseases.⁸⁶⁻⁸⁸

REFERENCES

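### The between-race genetics objective has no analysis behind it, and a non-significant genetics test would not show that genes fail to explain a C4 difference

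*Combined protocol and SAP*

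**What the plan says.** **Objective.** The short-term objective in *Specific Aims* ends with the statement that "we will study racial differences in specific C3 polymorphisms and C4 gene copy number".

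**Interpretation.** *Limitations* says: "An extremely interesting finding would be racial differences in complement levels without significant difference in complement genetics". The next sentence takes such a finding as a sign that lifestyle may contribute. The same section says that social and lifestyle differences are outside the study.

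**Background.** *Complement genetics* says that low C4 copy number goes with lower serum C4. *Racial differences in cardiometabolic risk and complement* describes a study of Black and White adults from central Ohio with strong correlations in each race between "C4 protein levels and gene copy number of C4". It gives no coefficient. It also mentions racial differences in C4 copy number in relation to lupus, and in C3 allele frequency (C3S 93% versus 83%).

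**Planned analyses.**
- *Aim 1*: "Unpaired t-tests will be used to compare differences in C3 and C4 levels", and also risk factors. Analysis of covariance is conditional and, in context, covers age and BMI. The regressions relate complement levels to risk factors.
- *Aim 2*: C3 variants against cardiometabolic measures, within African-Americans.
- *Aim 3*: C4 copy number against cardiometabolic risk, in African-Americans. C4 level is not among the listed outcomes.

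**Data.** *Complement genotypes* has C4 copy numbers and the three C3 variants typed for all subjects of this study. *Preliminary Studies* reports C4 copy numbers and C3 F-allele results for the white cohort, but nothing for rs11569562 or rs2250656.

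**The concern.** An objective and an interpretation both depend on comparing complement genetics between the races, and none of the three analysis sections supplies a test, estimate, model or sample size for it. Nor does any model ask how much of a racial difference in C4 goes with gene copy number, although the sponsor's own background treats copy number as a correlate of C4 level.

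The gap matters because of how it would probably be filled. The wording in *Limitations* invites two separate tests, one on levels and one on genes, with a significant result on the first and a non-significant result on the second read as evidence against a genetic contribution. That pairing does not support the reading. A modest copy-number difference can escape detection and still account for part of the level difference. With lifestyle unmeasured, nothing else in the study could correct the error.

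**Working it through.** **Inputs.**
- Group sizes, power and detectable difference, from the Aim 1 sample-size paragraph: 100 per race, and "we have power 0.8 to detect a 15% racial difference in C4 levels and 7.5% difference in C3 levels".
- White subjects so far reported, from *Preliminary Studies*: "Thirty-four of the 75 subjects were female".
- Alpha: not stated for Aim 1. I use the 0.05 given for Aims 2 and 3 and assume it is two-sided.
- Not given: the SD of C4, the SD or mean of copy number by race, and the correlation r between C4 level and copy number. I assume r = 0.3, 0.5 and 0.7.

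**1. The plan's own figure.** The detectable standardised difference for two means is (1.960 + 0.842) × √(1/100 + 1/100) = 2.802 × 0.1414 = 0.396 SD. Without the SD of C4, the 15% cannot be reproduced. Solved backwards it implies a coefficient of variation of 15/0.396 = 37.9%. The figure is neither confirmed nor contradicted. As a check on the convention, the Aim 3 statement (r = 0.28 with 99 subjects) does reproduce: (2.802/atanh 0.28)² + 3 = 97.8, so 98 are needed.

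**2. What a between-race copy-number test could detect.** The same formula gives 0.396 SD of copy number at 80% power. With 75 white subjects it is 2.802 × √(1/100 + 1/75) = 0.428 SD. For smaller differences with 100 per group, power = Φ(δ/0.1414 − 1.960):
- δ = 0.20 SD: 0.29
- δ = 0.28 SD: 0.51
- δ = 0.396 SD: 0.80, so missed one time in five

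**3. What a missed difference could carry.** If C4 rises linearly with copy number with within-race correlation r, a copy-number difference of 0.396 SD moves C4 by r × 0.396 of its own SD. Since 0.396 SD of C4 is the plan's 15%, the shift is r × 15%:
- r = 0.3: 4.5%
- r = 0.5: 7.5%
- r = 0.7: 10.5%

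These are illustrations under assumed r, not estimates of a real difference.

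**4. Effect of adjustment on precision.** If mean copy number is equal in the two races, the detectable difference becomes 15% × √(1 − r²):
- r = 0.3: 14.3%
- r = 0.5: 13.0%
- r = 0.7: 10.7%

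If copy number differs by 0.396 SD, each figure is multiplied by √(1 + 0.396²/4) = 1.019, giving 14.6%, 13.2% and 10.9%. The target is then the C4 difference at equal copy number, not the total difference.

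**The case against.** The best defence is that Aim 1 asks whether levels differ between the races, and the unadjusted comparison answers exactly that. Copy number lies on the path to C4 level, so adjusting for it estimates a different quantity. In the second part of Aim 1, whether complement levels account for racial differences in risk, the level matters whatever its source. The lifestyle remark is hedged, sits under *Limitations*, and is neither an aim nor a hypothesis. *Future Directions* says that cross-sectional correlations do not prove causation.

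All of that stands, and it limits the point to missing secondary analyses and an unsafe reading of one of them. It does not supply the analysis that the stated objective needs.

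Four stronger readings are tempting, and the documents do not support them:
- A reader might infer that no between-race genetics comparison is intended. The *Specific Aims* state one; what is missing is its analysis.
- A reader might infer that the unadjusted C4 comparison is wrong. It is valid for the question Aim 1 asks.
- A reader might infer that gene dosage could account for a particular share of a racial C4 difference. The documents give no copy-number means by race. They mention a racial difference only in connection with lupus, and subjects with autoimmune disease are excluded here. They also report that C4 yield per gene copy correlates with BMI, so strict proportionality cannot be assumed.
- A reader might infer that C3 should likewise be adjusted for F/S genotype. No section links F/S to C3 level; the variants said to affect C3 production are rs11569562 and rs2250656.

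**Conclusion.** The point holds in a limited form. The plan states a between-race genetics objective and offers an interpretation that relies on it, but specifies no analysis for either, and no model relates the C4 race difference to copy number. A non-significant genetics test could not fill the gap: it reaches 80% power only at about 0.40 SD of copy number with 100 per race, or 0.43 SD with 75 white subjects.

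The 0.40 SD figure rests on a two-sided 5% level and the planned group sizes. The C4 shifts in step 3 and the precision gain in step 4 rest on correlations that the documents do not give. The step 4 range of 14.3% to 10.7% also requires equal mean copy number in the two races.

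This is not a limit of the design. Copy number will be typed in this study and is reported for the white cohort, so the planned data should allow the missing analyses. The change should be made, but the Aim 1 comparison of levels does not depend on it.

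**What to change.** Keep the unadjusted C4 comparison as the answer to Aim 1, and add these secondary analyses:

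1. Between-race differences, with confidence intervals, in total C4, C4A, C4B, long and short copy number and in C3 F/S frequency. Include rs11569562 and rs2250656 only if the white cohort was typed for them.
2. The C4 race difference adjusted for total C4 copy number (or C4 per gene copy), beside the unadjusted difference, in subjects with copy number available.

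Then revise *Limitations*. The interpretation should rest on the adjusted difference and its confidence interval, not on a non-significant genetics test. State that lifestyle is not measured, so a residual difference is unexplained rather than attributable to lifestyle.

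The cost is some wording and a few extra models. The one practical risk is incomplete copy-number data in the white cohort: *Preliminary Studies* describes 75 subjects, while the Aim 1 sample size counts 100. The number with copy number available should be stated, and both C4 estimates reported in that same subset so that they can be compared.
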